1.2 Flow chat

2. Introduction

The incidence of gallstones has been increasing in recent years, up to 10-15% in developed countries, and is still increasing at a rate of 0.6% per year. It is estimated that common bile duct stones (CBDS) are present in about 10-20% of patients with symptomatic bile duct stones. Each year, common bile duct stones lead to acute complications such as biliary obstruction, cholangitis and acute pancreatitis in a large number of patients, seriously endangering their lives and health. In addition, Diagnostic Related Group (DRG) analysis shows that each episode of common bile duct stone costs \$9,000, and acute pancreatitis that progresses from common bile duct stones can result in 275,000 hospitalizations and \$2.6 billion in costs each year, imposing a significant

7 / 25

economic and health burden on society. Therefore, timely diagnosis of common bile duct stones and intervention for them are crucial. Endoscopic retrograde cholangiopancreatography (ERCP) is the method of choice for the diagnosis and treatment of CBDS, and guidelines recommend stone extraction for all patients with CBDS who are physically fit enough to tolerate ERCP operations. However, ERCP is a highly demanding and risky operation with the potential for serious complications such as PEP (incidence 2.6-3.5%). How to diagnose choledocholithiasis early and accurately, achieve timely patient intervention to improve prognosis, and avoid unnecessary medical operations to reduce risks are our current challenges to be solved.

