3.2. Exclusion criteria

All patients meeting the following criteria will not be considered for participation in the study:

- 1) Patients at high risk of common bile duct stones. High-risk patients are those with common bile duct stones detected by abdominal ultrasound, patients with manifestations of cholangitis or hospitalized patients with a history of gallbladder stones with pain, bile duct dilatation and jaundice;
- 2) Have drug or alcohol abuse or mental disorder in the last 5 years;
- 3) Pregnant or lactating women;
- 4) Altered anatomy due to previous history of upper gastrointestinal surgery;
- 5) Patients with advanced tumors resulting in abnormal upper gastrointestinal anatomy;

- 6) High-risk diseases or other special conditions that the investigator considers the subject unsuitable for participation in the clinical trial.

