4.1. Primary Endpoint

Accuracy of novice combined with AI-assisted and expert in the diagnosis of common bile duct stones in low to intermediate risk patients: ERCP and 6-month follow-up results as gold standard. A true positive was defined as CBD stones detected by EUS and the presence of CBD stones confirmed at ERCP; a false positive was defined as CBD stones detected by EUS and the absence of CBD stones confirmed by ERCP; a true negative was defined as CBD stones not detected by EUS and as CBD stones detected at 6-month follow-up; a false negative was defined as CBD stones not detected by EUS and subsequent ERCP or CBD stones were detected at 6-month follow-up.

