4.2. Secondary Endpoints

- 1) Sensitivity, specificity, NPV, and PPV for the diagnosis of common bile duct stones in low and intermediate risk patients
- 2) Detection rate of gallstone lesions
- 3) Missed detection rate of gallstone lesions
- 4) Detection rate of bile duct lesions(all bile duct lesions including gallstones)
- 5) Missed rate of bile duct lesion(all bile duct lesions including gallstones)
- 6) Number of bile duct standard station scans
- 7) Scan time

Incidence of Adverse Events

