6.3.4. Post-operative Managements

- 1) Routine postoperative care.
- 2) Subjects were observed until awakening.

- 3) Those without choledochal stones detected were followed up for 6 months (1st, 2nd, 3rd, and 6th months by telephone and instructed to review liver function and abdominal ultrasound).
- 4) Examination information, such as subject grouping, examining physician, examination time, sedation status, number of common bile duct stones found, and number of bile duct site scans, was recorded by the recorder.
- 5) Images, videos, and case data of the examination were collected.

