8.3. Sample Size Calculation

For the sample size determination, the level of bilateral significance was 5% ($\alpha=5\%$), 80% certainty ($\beta=20\%$), and based on previous reports of 90% diagnostic accuracy of endoscopists for common bile duct stones, a non-inferiority test of novice combined with AI non-inferiority to expert was performed, and a total of 147 patients were calculated to be enrolled. Assuming a 20% shedding rate, a total of 184 subjects were expected to be enrolled.

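### Section 4.1 omits the negation from the true-negative definition, so true and false negatives overlap and stone-free EUS-negative patients have no cell

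*Combined protocol and SAP*

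**What the plan says.** Section 4.1 names the reference standard as "ERCP and 6-month follow-up results as gold standard" and then defines the four cells. True and false positives depend on whether ERCP confirms the stone seen on EUS. For EUS-negative patients it says:

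- True negative: "a true negative was defined as CBD stones not detected by EUS and as CBD stones detected at 6-month follow-up".
- False negative: "a false negative was defined as CBD stones not detected by EUS and subsequent ERCP or CBD stones were detected at 6-month follow-up".

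Section 4.2 lists "Sensitivity, specificity, NPV, and PPV for the diagnosis of common bile duct stones in low and intermediate risk patients", which need the same cells. Section 6.3.4 adds that "Those without choledochal stones detected were followed up for 6 months", which shows what the follow-up is for but does not say how its result is scored. The Summary, Section 4.2 and Section 7.1 only name the endpoints. Section 8 does not define the cells.

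**The concern.** The true-negative and false-negative clauses both require a stone at 6 months, so they cannot separate a correct negative from a missed stone. The outcome that should make a negative correct, no stone on the reference standard, appears in neither.

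This is the only scoring rule for the primary endpoint. Accuracy, specificity and NPV use the true-negative count directly. Sensitivity is affected because the overlap can remove patients from the false-negative count. PPV uses only true and false positives, whose clauses are intact, so it is not affected.

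**Working it through.** **Classification.** The false-negative clause is itself garbled. It is read here as a stone found at a subsequent ERCP or at 6 months. For a reader whose EUS is negative (TN = true negative, FN = false negative):

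| ERCP | 6-month follow-up | Cell as written | Cell under the rewording proposed below |
|---|---|---|---|
| stone | stone | TN and FN | FN |
| stone | no stone | FN | FN |
| stone | missing | FN | FN |
| no stone | stone | TN and FN | FN |
| no stone | no stone | none | TN |
| no stone | missing | none | TN |
| not done | stone | TN and FN | FN |
| not done | no stone | none | TN |
| not done | missing | none | reference result missing |

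Every patient who meets the written true-negative definition also meets the false-negative one. Other readings of the false-negative clause could move some EUS-negatives who had an ERCP into that cell. The overlap remains on every reading, and stone-free EUS-negatives without ERCP still have no cell.

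**Size, as an illustration.** The plan states no figure for this point. Inputs:

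- N = 147 evaluable (Section 8.3).
- Sensitivity = specificity = 0.9. This is an assumption: Section 8.3 gives 90% for accuracy only.
- Prevalence p = 0.1, 0.2 and 0.4. These are assumptions, because the plan gives no prevalence for this population. Section 2 says "common bile duct stones (CBDS) are present in about 10-20% of patients with symptomatic bile duct stones", which is a different group, and Section 3.2 excludes "Patients at high risk of common bile duct stones".
- Every EUS positive is verified by ERCP, and every missed stone surfaces at ERCP or by 6 months (assumption).
- f = share of missed stones that are seen at 6 months and credited as true negatives, from 0 to 1.

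As shares of N, true positives = 0.9p, false positives = 0.1(1 − p), missed stones = 0.1p, and stone-free EUS-negatives = 0.9(1 − p).

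| Quantity | Formula | p = 0.1 | p = 0.2 | p = 0.4 |
|---|---|---|---|---|
| No cell | 0.9(1 − p) | 81% (119 of 147) | 72% (106) | 54% (79) |
| Overlap, at most | 0.1p × 147 | 1.5 patients | 2.9 | 5.9 |
| Literal accuracy, all patients | 0.9p + 0.1pf | 9–10% | 18–20% | 36–40% |
| Intended accuracy | 0.9p + 0.9(1 − p) | 90% | 90% | 90% |
| Literal specificity | pf / (pf + 1 − p) | 0–10% | 0–20% | 0–40% |
| Literal sensitivity | 0.9p / [0.9p + 0.1p(1 − f)] | 90–100% | 90–100% | 90–100% |
| Literal NPV | 0.1pf / 0.1p = f | 0–100% | 0–100% | 0–100% |
| Intended NPV | 0.9(1 − p) / [0.9(1 − p) + 0.1p] | 98.8% | 97.3% | 93.1% |

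Intended specificity and sensitivity are 90% by assumption.

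**Why restoring the negation alone is not enough.** Each patient is swept by both readers. Suppose one reader misses a stone, the other finds it, ERCP confirms and removes it, and the patient is stone-free at 6 months. If the true-negative clause asks only for no stone at 6 months, the reader who missed it is a true negative by that clause and a false negative by the ERCP part of the other. These are discordant pairs, which are what McNemar's test in Section 8.2 uses. The true-negative clause must therefore also exclude a stone at ERCP.

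**Missing reference results.** Section 8.3 says "Assuming a 20% shedding rate, a total of 184 subjects were expected to be enrolled". The arithmetic reproduces: 147 / 0.80 = 183.75, rounded up to 184. The allowance is 184 − 147 = 37 patients. The plan does not say that shedding means a missing 6-month result, so 37 is a ceiling on the number without one.

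**The case against.** The best reply is that this is a drafting or translation slip with only one sensible reading. The label itself, the gold-standard phrase, the contrast with the false-negative clause and the follow-up described in Section 6.3.4 all point to EUS-negative and reference-negative. No analyst would report 9% accuracy, so the illustration measures literalism rather than likely bias. It also depends on the denominator. Over classified patients only, literal accuracy is 0.9p to p divided by 0.1 + 0.9p, or 47–53%, 64–71% and 78–87% at the three prevalences. Few patients fall in the overlap.

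Most of this stands. The intent can be inferred, and the percentages describe the written rule rather than forecast the result. It does not remove the defect: the rule is wrong in the one place where the primary endpoint is defined, and nothing elsewhere corrects it.

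A second objection is that the proposed wording goes further than the missing word. That is true, but the two-reader example shows that the missing word alone would leave an overlap. EUS-positive patients without an ERCP result also have no cell. That is a separate gap, which this correction does not close.

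**Conclusion.** The concern holds and must be fixed. The true-negative definition cannot be applied as written: it lies wholly inside the false-negative definition and gives stone-free EUS-negatives no cell. That conclusion follows from the text and needs no numerical assumption. The size does: 54–81% of patients unclassified rests on the assumed 90% sensitivity and specificity, prevalence of 10–40% and complete verification. The likely effect on the reported result is small if the analyst scores by intent, but the plan should not leave its primary endpoint to inference.

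**What to change.** Reword Section 4.1 and apply it separately to each reader:

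- **True negative:** that reader's EUS shows no CBD stone, and none is found at ERCP or during follow-up, as verified by an ERCP result or a completed 6-month follow-up.
- **False negative:** that reader's EUS shows no CBD stone, but one is found at a subsequent ERCP or during the 6-month follow-up.
- **Missing reference result:** an EUS-negative patient with no stone found and with neither an ERCP result nor a completed 6-month follow-up is recorded as missing and is not counted as a true negative.

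The cost is two reworded clauses and one added sentence. No extra data or patients are needed, and the 147 evaluable and 184 enrolled are unchanged.

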4.2. Secondary Endpoints

- 1) Sensitivity, specificity, NPV, and PPV for the diagnosis of common bile duct stones in low and intermediate risk patients
- 2) Detection rate of gallstone lesions
- 3) Missed detection rate of gallstone lesions
- 4) Detection rate of bile duct lesions(all bile duct lesions including gallstones)
- 5) Missed rate of bile duct lesion(all bile duct lesions including gallstones)
- 6) Number of bile duct standard station scans
- 7) Scan time

Incidence of Adverse Events

4.3. Safety evaluation endpoints and other secondary endpoints

Adverse events shall be determined according to the definition in the code for the quality management of adverse events of medical devices. The following types of adverse events should be recorded and calculated in the hospital history and CRF. According to the CRF table, the

occurrence time, starting and ending time, intervention measures and treatment results should be filled in when recording. The severity should be referred to the previous literature and CTCAE 5.0 standard.

5. Purpose and overall design

5.1. Purpose

The purpose of this study was to evaluate the effectiveness and safety of the proposed deep learning-based bile duct sweep system in improving the diagnostic accuracy of common bile duct stones and reducing the rate of missed gallstones during bile duct sweeps by novice ultrasound endoscopists through a single-center, tandem, randomized controlled trial.

5.2. Overall design

This study is a prospective, single-center, tandem, randomized controlled clinical study. The study was conducted at the Renmin Hospital of Wuhan University, and the number of included samples was decided according to the specific experimental protocol, and 184 subjects were expected to be included.

6. Study process

6.1. Summary of Study Process

- If the patient meets the inclusion criteria, the patient is invited to participate in the study and then the informed consent procedure for the clinical trial is applied.
- Assess patients' eligibility based on the inclusion/exclusion criteria.
- If the patient meets the inclusion/exclusion criteria, information prior to endoscopy will be collected.
- A colonoscopy is performed after informed consent. Any intraoperative adverse events are recorded on the CRF for submission and subsequent analysis.
- Follow-up will be performed from the postoperative to the study completion, as detailed in the time and event table.

6.2. Enrollment

Only after patients signed the informed consent, can the research-related procedures be conducted.

6.2.1. Informed Consent

According to the Helsinki Declaration, patients are not allowed to participate in the study without adequate informed consent. The principal investigator is responsible for ensuring that no patient was enrolled in the study without adequate informed consent. Failure to obtain informed consent and failure to document this process is considered a violation of the Helsinki Declaration and the study protocol.

All informed consent documents (ICDs) must be approved by ethics. Patient's informed consent requires documentary record on the informed consent by himself in his primary language.

The investigator or trained designated person performs a preliminary screening to determine if the patient generally meets the eligibility criteria for the study. If yes, the investigator or trained designee should recommend the patient to participate in the study. If the patient agrees to participate, they will need to sign an informed consent document.

The investigator or trained designated person should confirm that the subject understands the following points in the study:

- the purpose of research,
- potential risks or adverse events,
- Potential risks or adverse events directly related to participating the research,
- The likelihood of failure,
- Research requirements include follow-up visits,
- All rights of the subject as a participant in the clinical study.

After explaining the purpose of the study, the investigator or trained designee should answer any questions from the subject. If the subject agrees to participate, his or her wishes must be recorded by signing and dated on the EC-approved ICF, and the document should be signed and dated by the patient receiving the informed consent.

After successful completion of the informed consent process, the investigator or trained designated person will assess the eligibility of patients based on the protocol.

6.2.2. Patient Selection

All patients who underwent Ultrasound Endoscopy, agreed to use artificial intelligence and generally meet the study requirements were screened based on the inclusion/exclusion criteria. Patients who passed the screening were enrolled and recorded in the subject screening and enrollment tables. There is no bias in the choice of the enrolled subjects. The date of screening, the results (enrolled or not), and the primary reason for not selecting subjects (such as not meeting inclusion criteria, or not interested in participating in the study) will be recorded.

After the patients are enrolled, the research center should complete the preoperative study data collection.

It is desirable to be able to collect complete data for all enrolled patients, without those withdrawal from the study.

6.2.3. Subject identification number

Patients were numbered after signing informed consent.

The subject number begins with EA as a fixed number and is numbered starting from 0001 at the time of signing the informed consent. For example, the first patient who signed the informed consent was EA0001, and the second one was EA0002.

Once the subject identification number is assigned, the number is not reusable.

6.3. Treatment Description

This section applies to individuals who have signed an approved informed consent and have been identified as eligible to participate in this study on the basis of the inclusion and exclusion criteria. This section introduces the preoperative, surgical and postoperative management of subjects in detail.

6.3.1. Patient Screening Assessments

- 1) History
- 2) Physical examination
- 3) Hematuria pregnancy test (if required)

6.3.2. Pre-Procedure Managements

- 1) Routine condition assessment.
- 2) Psychological counseling.
- 3) Perform routine patient anesthesia.

6.3.3. Intraoperative Managements

- 1) Subject position: lateral recumbent position with appropriate restraint.
- 2) Insertion route: chosen according to the subject's actual condition, usually transoral.
- 3) Bile duct sweep with novice followed by expert or expert followed by novice depending on the grouping.
- 4) Intraoperative abnormal findings must be scrutinized through standard clinical procedures, and photographs must be kept for documentation of any findings during ultrasound endoscopy.

6.3.4. Post-operative Managements

- 1) Routine postoperative care.
- 2) Subjects were observed until awakening.

- 3) Those without choledochal stones detected were followed up for 6 months (1st, 2nd, 3rd, and 6th months by telephone and instructed to review liver function and abdominal ultrasound).
- 4) Examination information, such as subject grouping, examining physician, examination time, sedation status, number of common bile duct stones found, and number of bile duct site scans, was recorded by the recorder.
- 5) Images, videos, and case data of the examination were collected.

6.4. Suspension and withdrawal

Patients who were screened and confirmed to be eligible for the study, signed the informed consent and completed the randomization were considered as enrolled. If serious program deviation, withdrawal, or death occurs, the subject study is considered to be suspended. If the subject discontinues the study after obtaining informed consent, the data before the discontinuation will still be included in the study-related analysis.

6.4.1. Pre-Procedure

In any time during the study period, even before colonoscopy, participants could withdraw their informed consent whenever necessary. Researchers can withdraw participants before surgery according to safety considerations in the inclusion and exclusion criteria.

6.4.2. Intraprocedure

For safety reasons, the investigator may have the subject quit during the procedure. For example, the patient is not suitable for receiving the instrument for the study or the endoscopists do not use the specified instrument for any reason. If the following serious cases occur, please withdraw during the operation:

- 1) Perforation
- 2) Bleeding
- 3) Allergy to narcotic drugs
- 4) The anatomical structure of the upper gastrointestinal tract is abnormal and the endoscopist cannot enter the scope smoothly
- 5) Inability to complete ultrasound endoscopy due to obstruction, intolerance, etc.
- 6) Unable to complete colonoscopy due to obstruction or other reasons

6.4.3. Replacement

Subject will be deemed to have commenced the study upon completion of the informed consent process, and any subject who has been discontinued prior to or during the endoscopic examination will not subsequently be replaced by other subjects.

6.5. Blindness and Uncovering Blindness

The study was blinded to the subjects, who were unaware of their grouping, and to the data review panel, whose members were unaware of the subjects' grouping.

Unblinding or blinding-breaking, i.e., presenting randomization results to subjects or evaluators, should be protected by the investigator whenever possible. Unblinding of randomization results for a single subject may lead to the disclosure of randomization results for other subjects, and any disclosure of randomization results can have a significant impact on the statistical analysis. Approach blinding disclosures with caution in general, and consider unblinding in the following circumstances:

- 1) Endangering the safety of the subject: For example, in some serious adverse events, the subject needs to know the randomization results to inform other physicians to take appropriate emergency treatment.
- 2) Endangering assessor safety: When the assessor faces a safety hazard and needs to know the randomization results.
- 3) Study compliance: For partial compliance reasons, disclosure of randomization results to the appropriate authorities or the public is required in specific circumstances, such as for unanticipated adverse events that require disclosure of the study system and the cases in which it is involved.
- 4) Other regulatory reasons.

7. Basis of study protocol and risk/benefit analysis

The use of a deep learning-based bile duct scanning system provides information to novice endoscopic ultrasound practitioners on the diagnosis and treatment of common bile duct stones, which does not provide a final diagnosis, the novice doctors make their own diagnosis and follow-up diagnosis and treatment on the basis of the tips from the bile duct site identification and common bile duct stones, in the end, the results of endoscopic sonography were compared with those of novices and experts, and the results of experts were taken into account when they were inconsistent.

7.1. Selection of endpoints

The primary evaluation endpoint was the accuracy of the diagnosis of common bile duct stones in low- and intermediate-risk patients by the novice combined with AI-assisted and expert. The secondary endpoints were sensitivity, specificity, NPV, and PPV of common bile duct stone diagnosis in low- and intermediate-risk patients; bile duct EUS sweep gallstone lesion detection rate; bile duct EUS sweep gallstone lesion miss rate; bile duct EUS sweep lesion detection rate (all bile duct lesions including gallstones); bile duct EUS sweep lesion miss rate (all bile duct lesions including gallstones); bile duct site Number of sweeps; sweep time; adverse event rate.

Adverse events in safety indicators shall be judged in accordance with relevant regulations, and serious adverse events shall be recorded and reported in accordance with regulations.

